7.1.2. Baseline Evaluation Visit (Visit 2) (All Subjects)

Baseline visit may occur up to one (1) month prior to procedure visit (Visit 3). This visit may be completed in conjunction with Visits 1 and 3. This visit is completed by all subjects.

The Investigator will view medical history and concomitant medications. Such history will also include information about previous treatments to further ensure compliance with the inclusion and exclusion parameters.

A detailed description of the visit assessments and evaluation methods are located in Section 7.2. The pre-intervention data collection will include the following:

1. Nasal Obstruction Symptom Evaluation (NOSE) Scale (See Section 7.2.1)
2. Epworth Sleepiness Scale* (See Section 7.2.3)
3. Baseline Health Economics Questionnaire* (See Section 7.2.4)
4. Demographics & Nasal Medical History (See Section 7.2.6)
5. Concomitant Medications (See Section 7.5)
6. Baseline Nasal Exam (See Section 7.2.7)
7. Modified Cottle Maneuver (See Section 7.2.9)
8. Lateral Wall Motion Video* (See Section 7.2.10)
9. Photography- Cosmetic* (selected sites only, See Section 7.2.11)
10. Photography- 3D* (selected sites only, See Section 7.2.12)
11. NAO Breathing Assessment (See Section 7.2.2)*
12. Assessment of Turbinate Hypertrophy Contribution to NAO (See Section 7.2.13)*

Note: Completion of assessments or evaluations noted with () is not required for training case subjects.*

Adverse events related to head and neck and/or respiratory conditions observed during the baseline visit and through visit 2 will be collected and documented. Spirox will be notified as necessary pursuant to the description provided in Section 8.

All data collected during baseline visits should be entered into the EDC no later than seven (7) days after completion of the study visit. Upon completion of the baseline visit, the subject will be scheduled for Treatment Visit (Visit 3).

7.1.3. Treatment Visit (Visit 3) (All Subjects)

This visit may be completed in conjunction with Visits 1 and 2, and should take place within 1 month after Visit 1 (Screening & Enrollment Visit). This visit is completed by all subjects.

If treatment occurs more than 1 month after Visit 1, inclusion and exclusion criteria must be re-confirmed and the subject will be asked to re-review, initial and date the ICF to continue participation. Subjects will also complete a NOSE scale.

Procedures conducted under this study protocol must be completed in an office setting using sterile technique. In addition to local anesthesia, subjects may receive monitored anesthesia care (MAC) or conscious sedation per the site's standard of care practice. Only procedure-trained investigators that are authorized by the sponsor will be allowed to place the devices during this study.

Optionally, an oral anxiolytics (e.g. Valium, Ativan or equivalent) and/or analgesic (e.g. Tylenol, or Tylenol with Hydrocodone) may be offered to the subject prior to the procedure, per the investigator's discretion.

If the subject has agreed to provide a testimonial (see Section 7.2.16), video may be captured during the procedure visit.

The below section includes a description of the activities occurring during the Index procedure visit and placement of the Latera™ Implants:

1. Amoxicillin or equivalent antibiotic may be administered to the subject before the procedure.
2. If planned treatment includes turbinate reduction, it must be completed prior to implant placement per site's standard of care procedure.
3. The skin of the nose and the mucosal surface should be cleaned with an antiseptic solution (e.g. isopropyl alcohol or betadine ophthalmic) prior to Latera Implant(s) placement.
4. The nasal anatomy will be examined and target trajectory for the Implant(s) should be established and marked with the aid of a sterile pen and sterile implant positioning guide per IFU (**Appendix III**).
5. Images of planned placements will be captured.
6. The following local anesthesia steps may be considered per site's standard of care procedures to ensure subject comfort during implant placement.
 - a. SPRAY: Anesthetic (e.g. Lidocaine or equivalent) or decongestant (e.g. Afrin or equivalent) may be sprayed into the nose.
 - b. TOPICAL: Few minutes after application of the spray, cotton balls or pledges soaked in anesthetic (e.g. Tetracaine, 4% lidocaine/mixed with Afrin, or equivalent) may be placed in the nasal vestibule, ensuring contact with turbinate and floor of nose posteriorly, and to lateral nasal wall anteriorly) for approximately 10 minutes.
 - c. INFILTRATION:
 - i. Anesthetic, such as Lidocaine with Epinephrine or mixture of Lidocaine/ Epinephrine mixed with Marcaine with Epinephrine, or the equivalent, may be injected locally.

- ii. The anesthesia may be injected to achieve an infraorbital block.
- iii. In addition, anesthesia may be injected along the proposed implantation track, starting at the alar rim and progressing to the supra-periosteal region of the maxilla. Additional injections into alar rim may also be considered.

7. The treatment area should also be pre-treated with an antibiotic ointment (e.g. Muciprocin or equivalent) to minimize potential risk of infection.
8. The Implant(s) (unilateral or bilateral) will be delivered per Spirox IFU20680 (**Appendix III**).
Note: Only one Implant per side may be placed.
9. Step 8 will be repeated if the subject requires bilateral implant placement.

All medications used during the procedure and resource utilization will be recorded. Adverse events observed during this visit will be collected and documented. Spirox will be notified as necessary pursuant to the description provided in Section 8. Data collected for the Treatment Visit should be entered into the EDC no later than even (7) days after the completion of visit.

IMPORTANT: Prior to discharge, subjects will be provided with the post procedure reminder form (**Appendix IV**). In addition, a course of antibiotics (e.g. Amoxicillin, Augmentin or equivalent) may be prescribed by the physician pursuant to standard medical practice guidelines.

Planning images captured during procedure will be transferred to sponsor via BrickFTP.com (See Section 7.2.10 for information on BrickFTP).

Upon completion of the treatment visit, the subject will be scheduled for the Follow-Up Visit.

7.1.4. 1 Month Follow-Up Evaluation Visits (Visit 4) (All Subjects)

Safety and performance data will be collected at 1 month (+/- 7 days) post procedure. This visit is completed by all subjects. A detailed description of the visit assessments and evaluations are located in Section 7.2. The following data will be collected:

1. NOSE scale (See Section 7.2.1)
2. NAO Breathing Assessment* (See Section 7.2.2)
3. Epworth Sleepiness Scale* (See Section 7.2.3)
4. Subject Satisfaction Questionnaire* (See Section 7.2.14)*
5. Post Procedure Health Economics Questionnaire* (See Section 7.2.5)
6. Concomitant Medications, if changed (See Section 7.5)
7. Adverse Events since last visit (See Section 8)
8. Post Procedure Nasal Exam (See section 7.2.8)
9. Lateral Wall Motion Video* (See Section 7.2.10)

Completion of assessments or evaluations noted with () is not required for training case subjects*

All data collected for these visits should be entered into the EDC no later than seven (7) days after the completion of each visit. For adverse events observed during these follow-up visits, Spirox will be notified as necessary pursuant to the description provided in Section 8.

Training subject participation will be complete at the 1 month follow-up time point and subjects will exit the study.

All non-training case subjects, upon completion of the follow-up visit activities, will be scheduled for the 3 Month Follow-up Evaluation Visit (Visit 5).

7.1.5. 3 – 24 Month Follow-Up Evaluation Visits (Visits 5-9) (All Subjects excluding training cases)

Safety and performance data will be collected at 3 months (+/- 15 days), 6 months (+/- 15 days), 12 months (+/- 30 days), 18 months (+/- 30 days), and 24 months (+/- 30 days) post procedure. These visits are completed by all non-training case subjects.

A detailed description of the visit assessments and evaluations are located in Section 7.2. The following data will be collected:

1. NOSE scale (See Section 7.2.1)
2. NAO Breathing Assessment (See Section 7.2.2)
3. Epworth Sleepiness Scale (See Section 7.2.3)*
4. Subject Satisfaction Questionnaire (See Section 7.2.14)*
5. Post Procedure Health Economics Questionnaire (See Section 7.2.5) *
6. Concomitant Medications, if changed (See Section 7.5)
7. Adverse Events since last visit (See Section 8)
8. Post Procedure Nasal Exam (See section 7.2.8)*
9. Lateral Wall Motion Video (See Section 7.2.10) *
10. Photography – Cosmetic (select sites only) – 3 and 6 Month Visits only (See Section 7.2.11)*
11. Photography – 3D (select sites only) – 3, 6 and 12 Month Visits only (See Section 7.2.12)*

*This assessment/evaluation will not be collected at the 18 and 24 month follow ups.

All data collected for these visits should be entered into the EDC no later than seven (7) days after the completion of each visit. Adverse events observed through the 12 month visit will be collected and documented. Only adverse device effects will be collected beyond the 12 month visit. Spirox will be notified as necessary pursuant to the description provided in Section 8. Data collected for these visits should be entered into the EDC no later than seven (7) days after the completion of each visit.

Upon completion of the follow-up visit activities, the subject will be scheduled for the next Follow-up Evaluation Visit.

Subject participation will be complete at the 24 month follow-up time point and documented in the Study Exit eCRF.

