4.2.2. SECONDARY ENDPOINTS

1. Proportion of treatment responders at 1, 3, 12, 18 and 24 months post procedure.
2. Change in nasal airway obstruction from baseline to 1, 3, 6, 12, 18 and 24 months as reported by subjects on the VAS scale.
3. Subject satisfaction questionnaire at 6 months.
4. Procedure and device-related adverse events through 24 months.

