8. ASSESSMENT OF SAFETY

8.1. SPECIFICATION OF SAFETY PARAMETERS

All Serious Adverse Events (SAE), Adverse Device Effect (ADE) and Serious Adverse Device Effects (SADE) will be collected and documented through the end of subject participation in the study. In addition, all non-serious device and procedure-related Adverse Events (AE) and all non-serious head and neck, and/or respiratory related AEs will also be collected and documented.

The primary safety endpoint evaluation will consider nasal procedure related and Latera related adverse events through 6 months post-procedure.

The following information for each AE, ADE, SAE and SADE will be collected:

- Date of onset
- Status and/or Outcome
- Date of resolution
- Adverse Event/Effect type (See Section 8.1.1)

In the event of Implant loss or removal, the following information will be documented:

- Implant exposed intranasal at pierce point or exposed on the external skin surface
- Implant retrieved by surgeon or subject
- Whether Implant loss or removal was complete or partial
- SAE or SADE (See Section 8.1.2 and 8.1.3)
- Severity of event (See Section 8.2.1)
- Relation to Study Device and/or procedure (See Section 8.2.2)
- Action taken
- Descriptive narration of Event/Effect

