8.1.2. DEFINITION OF ADVERSE EVENTS (AE) AND SERIOUS ADVERSE EVENTS (SAE)

An adverse event (AE) or effect is defined as any untoward and unintended medical occurrence experienced by a clinical study subject. An AE can therefore be any unfavorable and unintended sign, symptom, or disease temporally associated with the use of the investigational product, whether or not related to the product.

The following events will be considered to be serious adverse events (SAE) and must immediately and without delay (within 24 hours) be reported to the study Sponsor by fax and/or email. These events must be reported whether or not the Investigator believes they are related to study procedures, activities or device:

- Death (the investigator will provide a copy of any post-mortem findings, including histopathology reports if available).
- Life-threatening event or injury
- Disability – significant, persistent, or permanent change, impairment, or damage or disruption in the subject's body function/structure, physical activities or quality of life
- Necessitate immediate medical or surgical intervention to:
 - Preclude permanent impairment of a body function or permanent damage to a body structure; or
 - Relieve unanticipated temporary impairment or damage.
- Prolongation of a hospitalization
- Require new hospitalization

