8.3. TIME PERIOD AND FREQUENCY FOR EVENT ASSESSMENT AND FOLLOW-UP

The occurrence of an AE or SAE may come to the attention of study personnel during study visits and interviews of a subject presenting for medical care, or upon review by a study monitor.

All SAEs and all device and procedure-related AEs, including local and systemic reactions not meeting the criteria for SAEs, as well as all AEs related to head/neck and respiratory conditions occurring during the course of the study will be captured on the appropriate CRF.

Information to be collected includes event description, time of onset, Investigator's assessment of severity, relationship to study product (assessed only by those with the training and authority to make a diagnosis) or concomitant procedures, and time of resolution/stabilization of the event.

All SAEs and AEs will be followed to adequate resolution, or through the twenty-four month follow up visit.

Any medical condition that is present at the time of the participant's procedure will be considered as a baseline condition or comorbidity, and will not be reported as an AE. However, if the subject's condition deteriorates at any time during the study, and the condition is procedure/device related, it will be recorded as an AE. AEs will be recorded in the data collection system throughout the study.

Changes in the severity of an AE will be documented. AEs characterized as intermittent require documentation of onset and duration of each episode.

At each study visit, the Investigator will inquire about the occurrence of AE/SAEs since the last visit. Events will be followed for outcome information until resolution or stabilization.

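### After month 12 the visit text collects only adverse device effects, but Section 8, secondary endpoint 4 and the safety tables need more through month 24

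*Combined protocol and SAP*

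**What the plan says.** Two rules for months 12 to 24 stand in the current protocol text.

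- **Narrow rule.** The closing text of 7.1.5 has adverse events collected through the 12 month visit and then states: "Only adverse device effects will be collected beyond the 12 month visit".
- **Broad rule, in several places.**
  - In the 7.1.5 visit list, item 7 reads "Adverse Events since last visit (See Section 8" and carries no asterisk. The footnote to asterisked items is "This assessment/evaluation will not be collected at the 18 and 24 month follow ups".
  - Section 8.1 says that serious adverse events, adverse device effects and serious adverse device effects "will be collected and documented through the end of subject participation in the study".
  - Section 8.1.2 says of serious adverse events: "These events must be reported whether or not the Investigator believes they are related to study procedures, activities or device".
  - Section 8.3 covers serious events and device- and procedure-related events, "as well as all AEs related to head/neck and respiratory conditions occurring during the course of the study will be captured". It also has the investigator ask about events at every study visit.

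Two outputs depend on the answer. Secondary endpoint 4 (4.2.2) is "Procedure and device-related adverse events through 24 months". Section 10.4.4 calculates the incidence of adverse events, serious adverse events, fatal events and device-related events for the acute phase, through 6 months, and for all of follow-up.

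**The concern.** The narrow rule uses the word only, so a site that obeys it stops recording anything that is not a device effect at month 12. A site that obeys Section 8 continues. The protocol does not say which section prevails.

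If all sites follow Section 8, endpoint 4 can be reported as written. If all follow the 7.1.5 text, the 24-month procedure-related incidence and the whole-follow-up rates of all, serious and fatal adverse events omit the non-device events of year 2. If sites differ, the rates mix two ascertainment rules. A low count in the second year could then mean few events or no collection, and the 24-month tables would not show which. Events that were never asked about may not be recoverable at analysis.

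**Working it through.** The documents give no figure to reproduce. The check compares the collection rules by type of event, for events with onset after month 12 in non-training subjects, who are followed to 24 months (Section 7).

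| New event after month 12 | 7.1.5 closing text | Section 8 | Output that needs it |
|---|---|---|---|
| Adverse device effects, including deployment problems and user error (8.1.3) | Collected | Collected (8.1, 8.3) | Endpoint 4; 10.4.4 |
| Serious events that are not device effects | Not collected | Collected (8.1, 8.3); reportable whatever the cause (8.1.2) | 10.4.4 serious and fatal incidences |
| Turbinate-procedure events | Not collected | Collected (8.3) | Endpoint 4; 10.4.4 adverse-event incidence |
| Non-device head/neck and respiratory events | Not collected | Collected (8.3) | 10.4.4 adverse-event incidence |

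The rules agree only in the first row. The clearest clash is the second, because 8.1 names serious events and states their window.

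For endpoint 4 the gap is narrower. The device-effect definition in 8.1.3 covers deployment, so most events of the implant procedure itself should still be recorded. Section 8.2.2 makes the turbinate procedure a separate relationship type, and those events fall inside endpoint 4 but outside the narrow rule. Events that began earlier are not lost, since 8.3 says "All SAEs and AEs will be followed to adequate resolution, or through the twenty-four month follow up visit".

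The schedule table in 7.7.2 has separate rows for adverse events and adverse device effects. Its column alignment cannot be read reliably in the available text, so it is not used as evidence either way.

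**Scale of the endpoint 4 gap under the narrow rule**

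Inputs:
- Main-study enrolment: up to 170 (5.3, 10.5).
- Stand-alone implant cases: at least 50 (Protocol Summary), with 50 anticipated (10.5).
- p: the share of turbinate-treated subjects whose first counted event is turbinate-related and starts after month 12. The documents give no value, so 0-5% is an assumption.

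Most subjects who could have a turbinate procedure: 170 − 50 = 120, and 120/170 = 70.6%.

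Understatement of the 24-month incidence = 120p/170:

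| p | Subjects missed | Understatement (percentage points) |
|---|---|---|
| 0% | 0 | 0 |
| 1% | 1.2 | 0.71 |
| 2% | 2.4 | 1.41 |
| 5% | 6 | 3.53 |

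If all sites follow Section 8, the understatement is zero. Missed non-device serious, head/neck and respiratory events are not sized, because nothing in the documents supports a rate.

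**The case against.** The strongest reply is that 7.1.5 and its visit list can be read together. Device effects are still collected at 18 and 24 months, so an asterisk on item 7 would itself be wrong; item 7 points to Section 8, and the closing text narrows what is recorded. That weakens the missing asterisk as evidence, although on its plain wording item 7 remains due at both visits. It does not remove the conflict with 8.1 and 8.3. Section 8.1.2 sets no time window of its own, so the timing conflict for serious events rests on 8.1 and 8.3.

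The size estimate can also be challenged, with some justice. The upper value of 5% has no anchor in the documents. Several turbinate risks in 2.3.2, such as edema, bleeding and crusting, would be expected soon after the procedure, and only a first counted event after month 12 changes cumulative incidence. The 71% is a ceiling on subjects exposed to the gap, on enrolled rather than completing subjects (5.3 targets 150 completers). Section 10.4.4 lists no separate procedure-related incidence, so the points apply to the rate implied by endpoint 4.

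Divergence between sites is a possibility and has not been shown. Sites share one data-capture system, and Section 9 provides for CRF review through study exit. That review checks the forms against whichever rule they embody. Full source verification in Section 9 is tied to data through 6 months, and 5.3 allows the 18 and 24 month contacts by telephone or mailed form, so capture depends on what the form asks. The later SAP could state the window, but it cannot supply events that were not collected.

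Finally, the consequence is limited: there is no safety hypothesis, and 10.4.9 treats everything beyond the primary endpoint as supportive.

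**Conclusion.** The concern holds. The 7.1.5 closing text contradicts 8.1 and 8.3, and if followed it leaves secondary endpoint 4 and the whole-follow-up incidences in 10.4.4 incomplete for months 12 to 24.

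For endpoint 4, at most 120 of 170 subjects could be affected through late turbinate events, assuming full enrolment and exactly 50 stand-alone cases. The understatement is unknown. It is 0 to 3.5 percentage points over the assumed 0-5%, and zero if every site follows Section 8. The loss of non-device serious and fatal events cannot be sized from the documents.

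The 6-month primary safety endpoint is untouched, and device effects are collected to month 24 under either reading. This should be corrected, but it does not threaten the trial's main conclusion.

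**What to change.** Bring 4.2.2, the 7.1.5 list and text, the 7.7.2 schedule, 8.1, 8.1.2, 8.3 and 10.4.4 to one rule for months 12 to 24. Either choice would be consistent:

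1. Record serious adverse events and procedure-related adverse events, alongside device effects, at the existing 18 and 24 month contacts. State explicitly whether head/neck and respiratory events continue, and word 8.3 to match.
2. Keep device effects only after month 12. Restate endpoint 4 and the 10.4.4 tables as device effects through 24 months and other categories through 12 months, and amend Section 8 accordingly.

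Under either choice, tabulate months 0-12 and 12-24 separately in 10.4.4, limiting the second interval to the categories actually collected.

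The cost is protocol and SAP wording plus IRB approval of the amendment (13.2). The first option also adds a question at contacts already scheduled and possibly small CRF changes. Because those contacts may be remote, and no nasal exam is scheduled at them, it should also say how the relationship to the procedure is assigned, since 8.2.2 gives that task to the investigator who examines the subject. Neither option adds visits or subjects.

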7.1.6. Implant Replacement Procedure (All Subjects excluding training cases)

In the event a subject experienced an implant(s) retrieval prior to their scheduled 3 month visit, which was not due to a physiologic rejection or an allergic reaction to the material, a subject may voluntarily undergo an in-office procedure to have a new Latera Implant(s) placed.

The 3 Month Follow Up visit should be completed prior to re-implantation. Replacement of the implant (i.e., re-implantation) should occur at least thirty (30) days after the device has been retrieved and within three (3) to five (5) months from the initial index procedure. One re-implantation procedure per side may be completed during the study period.

Subjects indicating that they would like to proceed with the re-implantation procedure will be asked to sign an Informed Consent Form (ICF) Addendum that has been approved by the governing IRB. The implant procedure should be followed as described in Section 7.1.3, without any concomitant procedures. Procedure must be completed in an office setting, using sterile technique. In addition to local anesthesia, subjects may receive monitored anesthesia care (MAC) or conscious sedation per the site's standard of care practice.

The subject will continue study participation at the 6,12, 18 and 24 Month Follow-up Visits (Visits 6, 7, 8 and 9), as outlined in section 7.1.5.

No additional compensation will be provided to the subject for this procedure/visit.

Training case subjects may not have an implant replaced during study participation.

